Idiopathic pulmonary fibrosis (IPF) is defined as a specific form of chronic, progressive fibrosing interstitial pneumonia of unknown cause, occurring primarily in older adults, limited to the lungs, and associated with the radiologic and/or histopathologic pattern of usual interstitial pneumonia (UIP). The definition of IPF requires the exclusion of other forms of interstitial pneumonia including other idiopathic interstitial pneumonias and interstitial lung disease (ILD) associated with environmental exposure, medication, or systemic disease (American Thoracic Society and European Respiratory Society 2002).

The classification of interstitial lung diseases (ILDs) requires multidisciplinary expertise with input from various clinical experts, including pulmonologists, thoracic radiologists, and lung pathologists (Ryerson and Collard 2013).

Symptoms of IPF have usually been present for at least 6 months before the diagnosis is made. The initial clinical presentation is typically that of slowly progressive dyspnea and nonproductive cough. Digital clubbing occurs in up to 50% of patients. Lung auscultation reveals fine end inspiratory crackles, initially at the base of the lung and ultimately diffusely (Raghu et al. 2011). In advanced disease, features of right heart failure develop. Pulmonary function tests demonstrate a restrictive pattern, with a decrease in carbon monoxide diffusing capacity (DL_{CO}), and oxygen desaturation on exertion. Chest radiographs show diffuse interstitial opacities with volume loss, and high-resolution computed tomography (HRCT) scans show a characteristic pattern of peripheral (subpleural), bibasilar, reticulonodular abnormalities associated with architectural distortion, honeycomb changes, and traction bronchiectasis (Raghu et al. 2011, Raghu et al. 2018).

The diagnosis of IPF carries a bleak prognosis, with progressive disability due to respiratory insufficiency (Hallstrand et al. 2005). Data from the placebo arm of several controlled clinical trials suggest that the rate of decline in forced vital capacity (FVC) in patients with IPF is approximately 150 to 200 mL/yr in patients with IPF (Demedts et al. 2005; Ley et al. 2011; Raghu et al. 2004, 2008). Estimated survival, in the absence of treatment, is between three to five years after diagnosis (American Thoracic Society and European Respiratory Society 2002; Bjoraker et al. 1998; Douglas et al. 2000; Gribbin et al. 2006; Hyldgaard et al. 2014; Kim et al. 2006; Mapel et al. 1998; Olson et al. 2007).

A diminished quality of life in patients with IPF is well established, with impaired energy level and decreased level of independence in concert with respiratory symptoms (Swigris et al. 2005).

To date, two anti-fibrotic drugs have been approved for use in IPF: pirfenidone and nintedanib; both therapies have shown to significantly slow the progression of lung function decline in IPF (Raghu et al. 2015), although the disease remains incurable.

In terms of current clinical practice, there are limited data available on the early course of disease in symptomatic patients with suspicion of IPF/ILD. Thus, the peri-diagnosis period (see definition in Section 2.2) including the pre- and post-diagnosis periods is critical to the assessment of disease behavior, the timely accurate diagnosis and the decision to treat. The study will not focus on asymptomatic stages of disease when discovery would rely on imaging techniques for lung cancer screening purposes or incidental finding.

This study will characterize the disease behavior of IPF and ILD patient in the peri-diagnostic period, having as aim to increase the knowledge of the progressive nature of IPF/ILD already at early phases of assessment.

This objective will be achieved using a multidimensional approach assessing changes in pulmonary function, measured by daily handheld spirometry as well as assessing physical functional capacity.

2. STUDY DESIGN

2.1 PROTOCOL SYNOPSIS

The Protocol Synopsis is in Appendix 1 and the Schedule of Assessments in Appendix 2. For additional details, please see the Protocol Version 1, 26 April 2017 (and its Appendices).

2.2 OUTCOME MEASURES

By use of different outcome measures, a primary and multiple secondary and exploratory objectives will be investigated.

The primary objective of the study is to characterize the disease behavior of IPF during the peri-diagnostic period, where the peri-diagnostic period covers:

- the pre-diagnosis period (from inclusion into the study to diagnosis; for a maximum of 12 months).
- the post-diagnosis period (from the diagnosis to the start of drug treatment within 6 months or a maximum of 6 months after diagnosis if no treatment is started).

The investigation of the primary objective is based on Forced Vital Capacity (FVC) measurements in mL by daily home spirometry.

F. Hoffmann-La Roche Ltd
Statistical Analysis Plan MA39297, Final Version 2.0

Secondary objectives of the trial are:

- to characterize the disease behavior of non-IPF ILD during the peri-diagnostic period. This will be based on the investigation of FVC measurements in mL by daily home spirometry.
- to further characterize the disease behavior of IPF and non-IPF ILD in the peri-diagnostic period using a multidimensional approach. Hereby, a set of outcome measures will be used, which will be described in detail in the following sections.

Exploratory objectives of the trial are:

- Characterization of different subgroups
- Evaluation of the differences in FVC values at beginning of treatment, depending on reimbursement restrictions
- Evaluation of the collaboration platform
- Evaluation of the digital solution set up for the patients

Please note that the exploratory objective to evaluate the differences in FVC values at the beginning of treatment, depending on reimbursement restrictions as described in the CTP may be omitted in case that no countries with reimbursement restrictions will actually be taking part in the trial.

2.2.1 Primary Outcome Measures

Throughout the study, patients should perform a spirometry measurement of FVC [mL] at approximately the same time each day. For this purpose, study participants will be provided with a portable handheld spirometer and a tablet computer. Each spirometer will be factory calibrated.

The primary outcome measure is pulmonary function by use of FVC measurements in mL by daily home spirometry.

Note that for every FVC measurement the quality of the manoeuvre is monitored and documented according to acceptability criteria shown in the flow chart of Appendix [3](#). Depending on different characteristics of the blow, quality criteria will be provided to the patient and documented with the measurement (e.g. “blow out faster”, “blow out longer”).

Table 1 shows which of the quality criteria are considered acceptable and not acceptable manoeuvres.

Based on the Steering Committee (SC) feedback and in order to exclude the potential learning curve of each patient, the first 7 days of measurements per patient will be

removed from the analyses. All measurements will be taken into account for the analyses in case we have more than 1 per day.

Table 1 Quality criteria for FVC measurements

Not acceptable manoeuvre	Acceptable manoeuvre

 • Blow out faster • Blow out longer • Abrupt end 	
 • Don't start too early • Avoid coughing • Good blow

For analysis purpose only non-test acceptable manoeuvres flagged as 'Good blow' will be considered. In addition, any data point collected by the device before enrollment visit and after EOS visit, respectively, will be excluded from the analysis. In case a patient received treatment before EOS visit all data after treatment start date (inclusive site spirometry etc.) will be excluded from analysis as well. In order to consider only data points that are clinically meaningful FVC values outside a range from 400 ml to 6000 ml will also be excluded from analysis.

The corresponding primary endpoint used for the investigation of disease behavior of IPF is defined as the time-adjusted semi-annual FVC decline in patients with IPF during the peri-diagnosis period. Please refer to Section [4.5.1](#) for a detailed description of statistical analysis which is used for the computation of the primary endpoint.

2.2.2 Secondary Outcome Measures

2.2.2.1 FVC measurements

Additionally, to the daily spirometry measurements by the patients, FVC [mL] and in % predicted values should be assessed by site spirometry at every visit.

2.2.2.2 Physical function capacity

Patients will be asked to wear an accelerometer during the course of the study which provides information on their physical activity, such as steps per day and calorie expenditure. These daily measurements will be used to investigate the development of physical function capacity over time. The first 7 days of measurements per patient will be removed from the analyses as done with spirometry home data. In addition, any data point collected before enrollment visit up to start of treatment or EOS visit whatever occurred first will be deleted and for steps per day (SPD) a range for acceptable values from 200 to 20000 will be applied.

2.2.2.3 6MWT

The 6MWT measures the distance a patient is able to walk quickly on a flat, hard surface in a period of 6 minutes.

The 6MWT should be conducted at each patient visit, only at sites where a formalized process is available and the test can be performed under safe conditions.

2.2.2.4 Patient-Reported Outcomes (PRO)

Various paper-based PRO questionnaires and visual analog scales (VAS) will be used to monitor the patients' health status and well-being during the study.

- **King's Brief Interstitial Lung Disease (K-BILD) Questionnaire**

This questionnaire was specifically developed to analyze the health status of patients with ILD. The questionnaire consists of 15 items that have to be assessed by the patients on a scale ranging from 1 to 7, where 1 and 7 represent worst and best health status, respectively.

Items are compiled into three domains: breathlessness and activities, psychological, and chest symptoms. A detailed description how the total score and the domain scores are calculated can be found in [Appendix 4](#).

- **Modified Medical Research Council (mMRC) Dyspnea Scale**

The mMRC dyspnea scale is simple to administer and has been used for many years to grade the effects of breathlessness on daily activities. Grading will be done according to the following categories:

Grade 0	I only get breathless with strenuous exercise
Grade 1	I get short of breath when hurrying on the level or walking up a slight hill
Grade 2	I walk slower than people of the same age on the level because of breathlessness or have to stop for breath when walking on my own pace
Grade 3	I stop for breath after walking about 100 yards or after a few minutes on level ground
Grade 4	I am too breathless to leave the house

- **The EuroQol 5-Dimension Questionnaire (EQ-5D-5L)**

The 5-level version is a validated self-report health status questionnaire with two components:

- A five-item health state profile that assesses mobility, self-care, usual activities, pain/discomfort, and anxiety/depression. Each item is rated by the patient on a five-point scale where
 - Level 1: indicating no problem
 - Level 2: indicating slight problems
 - Level 3: indicating moderate problems
 - Level 4: indicating severe problems
 - Level 5: indicating extreme problems
- A unique health state is defined for each patient by combining the levels from each of the 5 dimensions. A total of 3125 possible health state profiles is defined in this way. Each state is referred to in terms of a 5 digit code, e.g. state 11111 indicates no problems on any of the 5 dimensions, while state 12345 indicates no problems with mobility, slight problems with washing or dressing, moderate problems with usual activities, severe pain or discomfort and extreme anxiety or depression. The health state of each patient can be converted into a single index value, presented by country specific value sets. SAS code including the respective index values for each of the possible 3125 health states for each country is available in order to convert health state profiles of each patient into index values as described above. Please note that an index value can only be derived in case ratings for all 5 dimensions are available. If for a patient a rating of one or more dimensions is missing, the index value is missing, too.
- A VAS that measures health state. The VAS is a 100 mm scale from worst (0 mm) to best (100 mm) health the patient can imagine.

For further information related to the EQ-5D-5L questionnaire, please refer to Appendix [Z](#).

- **Fatigue Assessment Scale (FAS)**

F. Hoffmann-La Roche Ltd
Statistical Analysis Plan MA39297, Final Version 2.0

The FAS is a fatigue questionnaire consisting of 10 items; five questions reflect physical fatigue and five questions analyze mental fatigue. A five-point scale (one for “never” to five for “always”) is used for patient responses. The scale score is calculated by summing all items. Therefore, the FAS scores can range from 10 to 50.

- **Cough / Urge to cough / Fatigue Visual Analogue Scales (VAS)**

The VAS are 100 mm scales on which patients indicate the severity of their cough, the urge to cough and their fatigue.

By use of the described secondary efficacy outcome measures the following secondary endpoints are defined and investigated:

- Change in pulmonary function tests from baseline (FVC measured in mL by daily home spirometry) for each diagnosis cohort.
- Change in pulmonary function tests from baseline (mL and % predicted FVC) by site spirometry for each diagnosis cohort
- Change in 6MWT from baseline over time for each diagnosis cohort
- Change in physical functional capacity (measured by daily home accelerometry, e.g. number of footsteps per day) from baseline over time for each diagnosis cohort
- Change in PRO measures from enrollment visit to diagnosis visit and EOS visit as well as change from diagnosis visit to EOS visit over time will be summarized for each diagnosis cohort.

2.2.3 Exploratory Outcome Measures

The following exploratory efficacy outcome measures will be documented by use of additional questionnaires:

- Evaluation of the collaboration platform by Investigators
- Evaluation of the digital solution set up for patients

2.2.4 Safety Outcome Measures

This study has no protocol mandated investigational medicinal product (IMP) or treatment requirements. Patients will stop the study prior to starting any drug treatment for IPF/ILD.

Any occurrence of non-elective hospitalization, Investigator-reported acute exacerbations, deaths, and events related to study assessments will be collected in the eCRF only.

Any untoward occurrences thought to be due to, or associated with, a commercial medicinal product used during the course of a patient’s standard medical treatment will not be reported in the eCRFs, but should be reported to the respective Market Authorization Holder or local Health Authority according to local regulatory requirements.

2.3 DETERMINATION OF SAMPLE SIZE

The main purpose of this study is hypothesis generation and estimation regarding the impact on pulmonary function in terms of the change in FVC, as measured by daily handheld spirometry, in patients suspected to suffer from IPF.

For this study, a total sample size of approximately 180 patients was planned (Table 2). The majority of the patients will be enrolled into two study cohorts, i.e., patients with a diagnosis of IPF or non-IPF ILD. Due to the uncertainty of the numbers of patients to be enrolled into these two cohorts, the sample size could not be derived for a certain patient number. For the purpose of sample size and power calculation, it was assumed that approximately 40% of patients will be diagnosed with IPF and 50% of patients will be diagnosed with non-IPF ILD. Approximately 10% of patients were expected to suffer from a disease other than ILD (non-ILD) or were expected not have a diagnosis within 12 months of enrollment. This assumption was based on published data (Wapenaar-deKorver et al. 2016).

Thus, it was expected to enroll approx. 72 patients with a diagnosis of IPF and approx. 90 patients with a diagnosis of non-IPF ILD. Approximately 18 patients may be diagnosed with non-ILD or have no diagnosis within the 12 months period following enrollment.

Table 2 Sample Size Scenarios

Number of patients with IPF	Mean FVC decline [mL] over 6 months	Lower Bound of 95% CI	Upper Bound of 95% CI	Total number of patients to be enrolled
72	25	8.83	41.17	180
72	50	33.83	66.17	180
72	75	58.83	91.17	180

CI = confidence interval

In Table 2 point estimates and 95% confidence intervals based on a normal distribution are tabulated for a range of possible outcomes, assuming 72 patients

analyzed, a standard deviation of 70 ml, and a precision of 16.17% (estimates produced using nQuery, version 7). A mean semi-annual FVC decline in the IPF group of 50 mL was considered to be a clinically relevant decline and a reasonable expectation in accordance with the literature (Ley et al. 2011). In addition, after inspection of historical data, it could be assumed that the common standard deviation in mean FVC decline was 70 mL as measured by handheld spirometry.

3. STUDY CONDUCT

The study conduct is described in Section 2.

3.1 RANDOMIZATION, BLINDING AND UNBLINDING PROCEDURES

Not applicable.

3.2 INDEPENDENT REVIEW FACILITY

Not applicable.

3.3 DATA MONITORING

Not applicable.

4. STATISTICAL METHODS

Categorical data will be summarized using frequencies and percentages (including a category for missing, if appropriate). Percentages will be based on the number of patients in each diagnosis cohort (a definition of different diagnosis cohorts is provided in Section 4.2.2), if not otherwise specified.

Continuous endpoints will be summarized using descriptive statistics (mean, standard deviation, minimum, 25th and 75th quartiles, median, and maximum).

Where applicable other analysis methods will be specified below.

4.1 ANALYSIS POPULATIONS

No analysis populations are defined in this trial. Data of all enrolled patients will be analyzed (enrolled patients have signed informed consent and passed all in- and exclusion criteria) by diagnosis cohorts, if possible.

Following thorough assessments and diagnoses, four groups of patients will be identified and allocated to one of the following diagnosis cohorts:

- Patients diagnosed with IPF (IPF patients)
- Patients diagnosed with an ILD other than IPF (non-IPF ILD patients)

F. Hoffmann-La Roche Ltd
Statistical Analysis Plan MA39297, Final Version 2.0

- Patients diagnosed with a condition that is not an ILD (non-ILD patients)
- Patients without diagnosis after 12 months assessments

4.2 TRIAL PERIODS, OBSERVATION AND ANALYSIS TIMES

The study consists of the peri-diagnosis period (from enrollment until end of study visit), which is divided into a pre- and post-diagnosis period (please refer to Sections [4.2.3](#) and [4.2.4](#) for the definition of these periods). Site visits will be conducted at a minimum at baseline, diagnosis, and end-of-study for each individual patient. During each study period, every patient should have at least one site visit, scheduled at the discretion of the investigator.

All patients will be managed at the discretion of the Investigator taking into account local clinical practice guidelines and standards of care as well as available clinical evidence for patients with suspected IPF/ILD or diagnosed with IPF/ILD.

4.2.1 Study Days

Study day is defined as the number of days since day of enrollment (Enrollment visit), i.e. Study day = Assessment date – date of enrollment + 1.

4.2.2 Baseline Observations

After discussion of the results of the first interim analysis from December 2018 with the SC in January 2019 it was decided to re-define the calculation for baseline FVC from home spirometry and steps per day from accelerometry. This new definition is given in Table 2 below.

Table 2 Definition of Baseline Observations

	Definition
Baseline data for site visit measurements	Baseline is defined as the measurement collected at the enrollment visit of each assessment.
Baseline data for home measurements	Baseline is defined as the average of the daily measurements collected during the next 7 consecutive days after the first 7 days removed, counted from the day of the first acceptable manoeuvre flagged as 'Good blow' of home spirometry after enrollment visit as defined in Table 1.

4.2.3 Pre-diagnosis Assessment Period

From inclusion into the study (enrollment visit), patients will be followed for a maximum of 12 months in the pre-diagnosis assessment period. The length of the pre-diagnosis period will be derived as follows:

Pre-diagnosis period = date of diagnosis – date of enrollment visit + 1
or
= date of end of study visit – date of enrollment visit + 1

where diagnosis date is taken from the IPF/ILD diagnosis eCRF page.

In case the diagnosis date and/or end of study visit is missing and no diagnosis is documented for the patient, the pre-diagnosis period will be set to the maximum of 12 months.

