4.2.5 End of Study

For individual patients, the end of the study will be as follows:

- Should no diagnosis be made 12 months after inclusion into the study, the patient will leave the study and perform the end of study visit
- Patients diagnosed with a non-ILD condition will leave the study on the date of diagnosis

- Patients diagnosed with IPF or non-IPF ILD will remain in the study and be followed up to the start of drug treatment (within six months) or a maximum of six months if no drug treatment is prescribed

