4.7 SAFETY ANALYSES

4.7.1 Safety Endpoints

The following safety endpoints will be analyzed descriptively by diagnosis cohorts:

- **Non-elective hospitalization, both respiratory and all cause:** a listing and a frequency table will be provided displaying number of patients with at least one non-elective hospitalization, the number of non-elective hospitalizations, the number of patients with at least one respiratory-related non-elective

hospitalization and the number of respiratory-related non-elective hospitalizations during pre- or post-diagnosis periods by diagnosis cohorts.

- **Investigator-reported acute exacerbations:** a listing and a frequency table will be provided displaying number of patients with at least one acute exacerbation and number of acute exacerbations during pre- and post-diagnosis periods by diagnosis cohorts. Additionally, number of patients and events will be given separately for triggered and idiopathic acute exacerbations. Acute exacerbation are defined as per Collard et al. 2016: answering No to the eCRF question “Is there an extra-parenchymal cause identified?”; and answering Yes to the eCRF question “Are there new, bilateral GGO (Ground glass opacification)/ consolidation on CT?” Please refer to [Appendix 8](#) for further information.
- **Death, all cause and respiratory-related:** a listing and a frequency table is given including number of deaths during pre- and post-diagnosis period, primary cause of death and frequencies with respect to autopsies performed.
- **Events related to the study assessments:** documented events will be coded with MedDRA version 21.1 or a higher one. Frequencies of events will be displayed by System Organ Class (SOC) and Preferred Terms (PT) by diagnosis cohorts. In addition, summary of the events characteristics, events by intensity and leading to study discontinuation will be presented separately. The tables will be provided for events occurring during the peri-diagnosis period. If the start date of an event is after or on the day of the enrollment visit or it is ongoing at enrollment visit and the end date of the event is after the day of the initial diagnosis visit, the event belongs to the peri-diagnosis period. A listing with all events will be also presented.

If for any of the above mentioned events an incidence rate of more than 15% is observed, time to event analyses according to the method of Kaplan-Meier will additionally be provided.

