4.8 MISSING DATA

In general, missing data will not be imputed. Exceptions will be made for events related to study assessments and concomitant medications. Here, missing start or end dates will only be imputed for the determination of whether the event or medication is allocated to the pre-, post- or peri-diagnosis period or whether the medication is considered as previous, concomitant or post medication as defined in section [4.7.3](#).

For events related to study assessments it is not expected that in case of partially missing dates only the year is given. In case the start/end day of the event is missing it will be imputed with the first/last day of the respective month assuring that the start/end date is after the day of the enrollment visit. In case the date is completely missing, it will be assumed that the event occurred during peri-diagnosis period.

If the medication start date is partially missing the day and month will be imputed with the earliest possible date but not prior to the date of enrollment. If the medication end date is partially missing the day and month will be imputed with the latest possible date not after death or end of study (i.e. DEC for month and 28/29/30/31 for day). In case the start/end date of a medication is completely missing, it will not be imputed and the medication will be considered a concomitant medication.

F. Hoffmann-La Roche Ltd
Statistical Analysis Plan MA39297, Final Version 2.0

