Appendix 2 Schedule of Assessments

	Enrollment (Suspicion of IPF/ILD) [Baseline visit]	Pre-diagnosis Assessment period (max 12 months) ^a [Visit 1]	Day of initial Diagnosis [Visit 2]	Post-diagnosis Assessment period (max. 6 months) ^a [Visit 3]	End of study / Early termination ^b [End of Study visit]
Informed consent ^c	x				
Review of inclusion/exclusion criteria	x				
Demographic data	x				
General medical history and baseline conditions	x				
Physical examination:					
Vital signs and weight	x	x	x	x	x
Height and body mass index (BMI)	x				
Disease-relevant data, as available ^d	x	x	x	x	x
Home-based assessments:					
Daily spirometry ^e	x	x	x	x	x
Daily physical functional capacity assessments ^f	x	x	x	x	x
PRO ^g	x	x	x	x	x
Site assessments:					
FVC	x	x	x	x	x
6MWT ^h	x	x	x	x	x
Serum sample for biomarker assessment (optional) ⁱ	x				
Whole blood sample for biomarker assessment (optional) ⁱ	x				
Concomitant medications ^j	x	x	x	x	x

	Enrollment (Suspicion of IPF/ILD) [Baseline visit]	Pre-diagnosis Assessment period (max 12 months) ^a [Visit 1]	Day of initial Diagnosis [Visit 2]	Post-diagnosis Assessment period (max. 6 months) ^a [Visit 3]	End of study / Early termination ^b [End of Study visit]
Investigator / Patient survey					X
Non-elective hospitalizations, acute exacerbations, deaths, events related to study-assessments		X	X	X	X

6MWT=6-minute walk test; EQ-5D=EuroQoL Five-Dimension 5-level version; FAS=Fatigue Assessment Scale; FVC=forced vital capacity; ILD=interstitial lung disease; IPF=idiopathic pulmonary fibrosis; K-BILD=King's Brief Interstitial Lung Disease; mMRC=modified Medical Research Council. PRO=patient-reported outcome; VAS=Visual Analogue Scale.

^a The length of this period may vary on an individual basis. During these assessment periods, local clinical practice should be followed; however, at least 1 site visit has to be performed.

^b End of study for an individual patient:

- Should no diagnosis be made 12 months after inclusion into the study, the patient will leave the study.
- Patients diagnosed with a non-ILD condition will leave the study on the date of diagnosis.
- Patients diagnosed with IPF or ILD will remain and be followed in the study up to the start of drug treatment (within six months) or a maximum of six months if no drug treatment is prescribed

^c Informed consent must be documented before any study-specific procedures are performed.

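### Section 4.2.3 can credit undiagnosed patients with 12 months of pre-diagnosis time that was not observed (minor; descriptive output only)

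*SAP*

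**What the plan says.** SAP Section 4.2.3 offers two formulas for the pre-diagnosis length. The first runs from enrollment to the diagnosis date. The second, for use without a diagnosis date, is "date of end of study visit – date of enrollment visit + 1".

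The section then adds a fallback: "In case the diagnosis date and/or end of study visit is missing and no diagnosis is documented for the patient, the pre-diagnosis period" takes a fixed value. The end of the sentence gives that value: "no diagnosis is documented for the patient, the pre-diagnosis period will be set to the maximum of 12 months".

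Other sections bear on who meets this fallback:

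- Section 4.2.5, on patients still undiagnosed at one year: "Should no diagnosis be made 12 months after inclusion into the study, the patient will leave the study and perform the end of study visit".
- Appendix 2 has a visit column headed "End of study / Early termination", so patients who leave early also have a closing visit planned.
- Section 4.7.1 expects that some deaths may fall before diagnosis: "a listing and a frequency table is given including number of deaths during pre- and post-diagnosis period".
- Section 4.4.1 tabulates premature discontinuations with their reasons.

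The derived length is used in Section 4.4.3.4, which summarizes the durations of the pre- and post-diagnosis periods. Section 4.5.5 repeats that summary for certain subgroups in the final analysis.

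**The concern.** The opening of Section 4.2.3 treats 12 months as a ceiling on follow-up. The fallback turns that ceiling into an assigned value. For someone who left undiagnosed before month 12, the duration table would then show time during which the patient was not in the study.

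The trigger is also ambiguous. Two programmers could follow the same sentence and produce different tables: one with every undiagnosed patient at exactly 12 months, the other with EOS-based lengths for all but the few who have no EOS visit.

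At stake is the accuracy of a descriptive summary of how long patients were observed before diagnosis. No inferential result depends on it.

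**Working it through.** The SAP gives no figure for this quantity, so there is nothing of its own to reproduce. The check has a logical part and an arithmetic part.

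**Which patients meet the fallback.** Let A = diagnosis date missing and B = EOS visit missing. Consider only patients with no documented diagnosis. For them A is always true.

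| Reading of the trigger | Condition | Undiagnosed patients given 12 months |
|---|---|---|
| Literal (and/or) | A or B | all, even with a recorded EOS date |
| Both dates missing | A and B, which reduces to B | those without an EOS visit |
| EOS visit missing | B | those without an EOS visit |

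There are therefore two distinct readings. Under the literal one, the EOS-date formula is overridden for undiagnosed patients and their durations have standard deviation 0. Under the narrow one, the formula holds and the fallback reaches only patients with no EOS visit. Sections 4.2.5 and Appendix 2 plan a closing visit for completers and early leavers, so this leaves mainly patients who died or were lost, plus any who stayed 12 months and missed the last visit. Only for the last of these is 12 months about right.

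**Size per patient.** For last observation at month m the overstatement is 12 − m months. Taking 12 months as 365 days and a month as 30.4375 days (both assumed; the SAP does not state 12 months in days):

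- m = 2: 12 − 2 = 10 months; 365 − 61 = 304 days
- m = 9: 12 − 9 = 3 months; 365 − 274 = 91 days

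Counting the + 1 day of the SAP formula in the observed length gives 365 − 62 = 303 and 365 − 275 = 90 days.

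**Size in a group mean.** If k of n undiagnosed patients are affected, the mean is too high by k(12 − m)/n. The SAP gives neither k nor m. Section 2.3 gives about 18 patients for non-ILD and undiagnosed together, so n = 18 is a planning ceiling for the undiagnosed alone. Under assumed k = 1 to 3 and m = 2 to 9:

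- smallest: 1 × 3 / 18 = 0.17 months
- largest: 3 × 10 / 18 = 1.67 months

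These are illustrations under assumptions, not estimates.

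**Where the value goes.** It enters the duration summary (4.4.3.4) and repeats of it that include undiagnosed patients, such as the one for patients with respiratory-related hospitalization (4.5.5). It does not enter the primary endpoint, which uses each IPF patient's regression slope on study day (4.5.1). Nor does it enter the time-to-diagnosis curves, which use diagnosed patients only (4.4.3.4).

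**The case against.** The strongest reply is that the contradiction rests on reading *and/or* literally. If a missing EOS visit was meant, the two rules are compatible. Even on the literal reading the EOS formula may keep a use. The diagnosis date comes from the IPF/ILD diagnosis page, and non-ILD patients leave on the day of diagnosis. If that page holds no date for them (the SAP does not say), the formula serves them, and the fallback is not triggered because a diagnosis is documented. For patients who reach 12 months undiagnosed, the assigned value is also about right. All of this stands, and it limits the point to loose wording plus a wrong value for early leavers. It does not remove the wrong value for a patient who died or was lost undiagnosed without an EOS visit.

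A reader might infer more, and the documents do not support it:

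- **Conflict with Section 4.8.** That section says "In general, missing data will not be imputed. Exceptions will be made for events related to study assessments and concomitant medications", so the 12-month value might look like a forbidden imputation. But the rule is stated as general, and Appendix 4 imputes missing K-BILD items as well, so a section-specific rule is not clearly a breach. The bound "the latest possible date not after death or end of study" is written for partially missing medication end dates, not for period lengths.
- **Carry-over to the progression subgroups.** Section 4.4.3.3 assigns progression over the whole peri-diagnosis period, and Section 4.5 limits peri-diagnosis analysis of daily measurements to IPF and non-IPF ILD patients. Undiagnosed patients may not be in those tables. ILD subgroups consist of diagnosed patients by definition.
- **A large shift in the mean.** A figure such as 3 × 10 / 9 = 3.33 months needs three of only nine undiagnosed patients lost at month 2 with no early-termination visit. Nothing in the SAP suggests that.
- **A defect in the time-to-diagnosis analysis.** Section 4.4.3.4 openly restricts it to diagnosed patients, which is a valid description conditional on diagnosis. The table of objectives and endpoints in Appendix 1 lists no endpoint that needs an all-enrolled estimate. Such an output would be an optional extra.

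**Conclusion.** The point holds as a minor one. The fallback in Section 4.2.3 is ambiguous, and on either reading it gives too long a pre-diagnosis period to a patient who died or was lost undiagnosed before month 12 without an EOS visit. The literal reading extends this to undiagnosed early leavers who do have an EOS date.

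The excess per patient is 12 − m months, about 304 to 91 days for last observation at months 2 to 9. That range of m is assumed. The number of patients affected is not in the SAP and is probably small, because closing visits are planned for early leavers too. The effect on any group mean therefore cannot be fixed in advance. That the assigned value is wrong for these patients does not depend on any of these assumptions.

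**What to change.** Replace the fallback sentence in Section 4.2.3 with:

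*For patients without a documented diagnosis: EOS visit date − enrollment date + 1. If there is no EOS visit: date of death, otherwise last available visit or last home measurement, − enrollment date + 1. Twelve months is a cap only.*

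This removes *and/or* and settles both readings. Giving the cap in days would avoid a second small ambiguity.

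The cost is one sentence and a small change to one derived variable. The sources are ones the SAP already uses: deaths are recorded in the eCRF (2.2.4), Section 4.4.3.4 already falls back on the last available visit for censoring, and home measurements carry a study day (4.5.1). The wording does not rely on a last-contact date, because the SAP does not mention one. No new output is needed.
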